12.2.1 Interim analyses

As outlined in the DSMB procedure, planned interim analyses will occur to evaluate safety after the enrollment of 10 subjects and after the enrollment of 20 subjects.

12.2.2 Determination of sample size

For the power analysis, the 4-day estimates of failure to defecate (i.e., failure to have a SBM) from the Kaplan-Meier plot presented in the Guardiola et. al. paper [4] was used as the estimate of lower GI tract paralysis. The figure below shows that the estimate of the percent of patients who failed to defecate (1 minus plotted proportion with defecation) by day 4 was 40% in the Prophylaxis group (i.e., the intervention group) vs. 90% in the non-prophylaxis (Treatment) group (i.e., the control group) (see yellow highlights in figure). We believe the 4-day estimate will be strongly related to the primary outcome of lower GI tract paralysis (≥ 3 days without a SBM).

90% (Placebo) vs. 40% (Prophylactic treatment), all subjects have complete follow-up, and the analysis is done using the log-rank test to compare survival curves. As sensitivity analysis, the table also shows the power of the study with this sample size under different scenarios. Because this is not the final definitive study to determine efficacy, a less stringent alpha of 0.10 may be justified for this Phase II proof-of-concept study which, if positive, would be followed by a confirmatory study [15]. While we expect most subjects to finish the study (based on the inclusion criteria), we have shown the impact on the power if approximately 20% of subjects do not finish the study. We have also varied the estimated proportion of patients failing to defecate by day 4 (i.e., not having a SBM) in the placebo group from 90% to 70% and in the prophylactic treated group from 40% to 50%.

Statistical Power of Log-Rank Test with n=18 subjects per group (36 total)

Complete study	ALPHA	Proportion Failing to Defecate at Day 4 (Placebo vs. Prophylactic Treated)				
		90% vs. 40%	90% vs. 50%	80% vs. 40%	80% vs. 50%	70% vs. 40%
100%	0.05	99.8%	98.4%	92.7%	76.0%	76.0%
	0.10	100.0%	99.4%	96.2%	84.9%	84.9%
80%	0.05	99.7%	97.6%	90.8%	72.5%	72.5%
	0.10	99.9%	99.0%	95.1%	82.2%	82.2%

For this Naloxogol randomized trial, we propose enrolling 36 subjects, 18 per group. The statistical power table below shows this sample size yields over 95% power using an alpha of 0.05 if the true day 4 estimated freedom of event (defecation) rates are

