12.2 Methods of statistical analysis

[figure not shown]
Baseline characteristics of patients will be compared using standard univariate methods (chi-square test, t-test) to confirm the randomization was successful in achieving comparable groups. To test the primary outcome (incidence of lower GI tract paralysis), given that there may be censoring (i.e., subject may die or withdraw from study before developing lower GI tract paralysis), we will present Kaplan-Meier curves for the naloxegol and placebo groups for the time to first development of lower GI tract paralysis (≥ 3 days without a SBM after study randomization) during the ICU stay up to 10 days and compare the curves using a log-rank test. If all subjects complete the study (e.g., no deaths, no withdrawal or loss-to-follow-up for other reasons), then we will instead compare the proportion of patients that develop lower GI tract paralysis after study randomization during the ICU stay up to 10 days between the naloxegol and placebo groups using a chi-square test. The secondary outcome, time to first SBM will be estimated using a Kaplan Meier time to event analysis and compared between groups using a log-rank test. The secondary outcome of the number of ICU days without a SBM will be compared between the naloxegol and placebo groups using the Poisson regression for count data and adjusting for total number of days in the ICU (up to a maximum of 10) as an offset term in the Poisson model. The secondary outcome of the average daily opioid requirements will be compared between groups using either a student t-test or nonparametric Wilcoxon rank-sum test if the assumptions of the student t-test fail to be met. Length of mechanical ventilation and ICU stay will be reported as medians and interquartile ranges and will be compared using the Wilcoxon Rank Sum Test. For all statistical tests of hypotheses, a two-sided p-value of ≤ 0.05 will be considered as statistically significant. As this is a Phase II proof of concept study a p value of <0.10 may still be worth consideration for future study, however. All statistical analyses will be performed using SPSS 17.0. (SPSS, Chicago, IL) or other comparable commercially available statistical software.

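### The 70% vs 40% column of the power table repeats the 80% vs 50% column in all four rows and overstates power there, by about 6 to 8 points if the horizon was 10 days

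*SAP*

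**What the plan says.** Section 12.2.2 fixes the size ("we propose enrolling 36 subjects, 18 per group") and states that power is computed on the basis that "the analysis is done using the log-rank test to compare survival curves". The base case is 90% (placebo) against 40% (treated) still without a spontaneous bowel movement at day 4.

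The table is offered as a sensitivity analysis. It varies the day-4 rates "in the placebo group from 90% to 70% and in the prophylactic treated group from 40% to 50" percent. It adds rows for incomplete follow-up ("we have shown the impact on the power if approximately 20% of subjects do not finish the study") and for a looser test level, arguing that "a less stringent alpha of 0.10 may be justified for this Phase II proof-of-concept study".

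The row for complete follow-up at alpha 0.05 is "99.8% 98.4% 92.7% 76.0% 76.0". Across the four rows, the 80% vs 50% column and the 70% vs 40% column both read 76.0, 84.9, 72.5 and 82.2%. The protocol and the SAP print the same values.

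Section 12.2.2 gives no power formula, follow-up horizon or dropout model. The nearest statement is the primary analysis in section 12.2, which follows subjects "during the ICU stay up to 10 days and compare the curves using a log-rank test".

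**The concern.** Both scenarios have a 30-point difference at day 4, but log-rank power does not depend on that difference. It depends on the hazard ratio and the number of events, and both change between the two columns. Exact agreement to one decimal in four rows, over two alpha levels and two levels of follow-up, is not what a calculation would give.

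The affected scenario is the least favourable in the table. If its entries belong to another scenario, the plan reports a better worst case than the design has. The printed table also leaves the impression that every cell at alpha 0.10 exceeds 80%.

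**Working it through.** **Inputs.** 18 per group, log-rank test and day-4 rates: section 12.2.2. Two-sided testing: section 12.2 ("a two-sided p-value of ≤ 0.05 will be considered as statistically significant"); alpha 0.10 is also taken as two-sided. Horizon of 10 days: inferred from the analysis window in section 12.2. Exponential times to first bowel movement, and exponential dropout reaching 20% by day 10 for the 80% rows: assumptions.

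**Formulas.** With S the proportion still without a bowel movement at day 4:
- hazard h = −ln(S)/4
- HR = ln(S treated)/ln(S placebo)
- expected events D over 10 days, complete follow-up = 18 × [(1 − S_placebo^2.5) + (1 − S_treated^2.5)]
- with dropout hazard g = −ln(0.8)/10, events per arm = 18 × h/(h+g) × [1 − exp(−10(h+g))]
- Schoenfeld power = Φ(√(D/4) × ln HR − z), with z = 1.960 for alpha 0.05 and 1.645 for alpha 0.10

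**80% vs 50%, which reproduces the plan.** HR = ln(0.5)/ln(0.8) = 3.106. D = 18 × [(1 − 0.572) + (1 − 0.177)] = 22.5. √(22.5/4) × ln(3.106) = 2.69. Power is Φ(2.69 − 1.96) = 76.7% and, at alpha 0.10, 85.2%. With dropout it is 73.1% and 82.4%.

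**70% vs 40%.** HR = ln(0.4)/ln(0.7) = 2.569. D = 18 × [(1 − 0.410) + (1 − 0.101)] = 26.8. √(26.8/4) × ln(2.569) = 2.44. Power is Φ(2.44 − 1.96) = 68.5% and, at alpha 0.10, 78.7%. With dropout D is about 24.7, giving 65.1% and 75.9%. The additional events do not offset the smaller hazard ratio.

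**Whole table, printed / recomputed (%):**

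| Complete, alpha | 90 vs 40 | 90 vs 50 | 80 vs 40 | 80 vs 50 | 70 vs 40 |
|---|---|---|---|---|---|
| 100%, 0.05 | 99.8 / 99.8 | 98.4 / 98.4 | 92.7 / 93.2 | 76.0 / 76.7 | 76.0 / **68.5** |
| 100%, 0.10 | 100.0 / 99.9 | 99.4 / 99.3 | 96.2 / 96.5 | 84.9 / 85.2 | 84.9 / **78.7** |
| 80%, 0.05 | 99.7 / 99.7 | 97.6 / 97.6 | 90.8 / 91.2 | 72.5 / 73.1 | 72.5 / **65.1** |
| 80%, 0.10 | 99.9 / 99.9 | 99.0 / 98.9 | 95.1 / 95.3 | 82.2 / 82.4 | 82.2 / **75.9** |

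The first four columns agree within 0.7 points. The last is too high by 7.5, 6.2, 7.4 and 6.3 points. Since 80% vs 50% reproduces, the wrong column is 70% vs 40%.

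**Simulation.** Log-rank simulation of 70% vs 40% under the same assumptions gives, in row order, 68.3, 78.7, 64.4 and 75.3% (100,000 trials) and 68.8, 79.0, 64.0 and 75.5% (20,000 trials). Over the two runs the overstatement is 5.9 to 8.5 points.

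**Sensitivity to the horizon** (Schoenfeld, complete follow-up, alpha 0.05):

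| Horizon (days) | 80 vs 50 | 70 vs 40 |
|---|---|---|
| 4 | 52.1 | 47.6 |
| 9 | 74.4 | 66.6 |
| 10 | 76.7 | 68.5 |
| 11 | 78.6 | 70.1 |
| 16 | 84.4 | 75.0 |
| 30 | 89.8 | 79.4 |

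Over these horizons and all four rows, 70% vs 40% lies below 80% vs 50% by about 4 to 11 points. A horizon near 16 days brings 70% vs 40% close to the printed 76.0% but puts 80% vs 50% more than 8 points above it. In row order, the 70% vs 40% column would be 66.6, 77.2, 63.0 and 74.2% at 9 days and 70.1, 80.0, 66.8 and 77.3% at 11 days. Those horizons miss the other 16 cells by up to 1.8 and 2.6 points.

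**The case against.** The strongest reply is that the horizon, formula and dropout model are all inferred, so the size of the error is conditional. That stands. The fit is close but not exact: Schoenfeld runs 0.2 to 0.7 points above the printed 80% vs 50% cells, and the larger simulation gives 71.5% for that scenario with dropout at alpha 0.05, against the printed 72.5%. The original program is therefore not identified, and the recomputed values are a guide.

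The gap between the two columns also depends on the formula. At 4 days with complete follow-up and alpha 0.05, Freedman's formula gives 44.5% and 42.4%, a gap of only 2.1 points. Treating failure as the event, and letting every subject have one, reverses the order (71.5% and 73.0%). Neither variant reproduces the table as a whole, and neither makes the columns equal, so the printed figures are not rescued.

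On importance, the table already prints values in the seventies, so a reader can see that power falls under pessimistic rates. The plan sets no power target for the sensitivity scenarios. It justifies alpha 0.10 by the proof-of-concept aim, not by the size of any cell, so falling below 80% breaches no stated criterion. No analysis or stopping rule uses this column. These points limit the consequence but do not make the four figures right.

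**Conclusion.** The concern holds. The 70% vs 40% column is wrong as written in both documents. The text shows that a 70% placebo rate was intended, so a mislabelled column is unlikely. The documents do not show how the duplication arose.

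On exponential times, a 10-day horizon and 20% exponential dropout, the worst-case power at alpha 0.05 is about 65%, not 72.5%. At alpha 0.10 the lowest value is about 76%, not 82.2%, and both 70% vs 40% cells fall below 80%. The duplication itself needs none of these assumptions. The headline claim of over 95% power for 90% vs 40%, the sample size of 36, the test and the alpha levels are unaffected. It should be corrected, but it does not call the design into question.

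**What to change.** Rerun the 70% vs 40% column with the program and settings used for the other four, and replace its four figures in section 12.2.2 of both the protocol and the SAP. Values near 68, 79, 65 and 76% are to be expected if the horizon was 10 days; the rerun, not this approximation, should supply the printed numbers. Add one sentence under the table giving the power formula or software, the follow-up horizon, the assumed survival shape and how the 20% non-completion was modelled.

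The cost is four numbers and one sentence in each document. N, alpha, the test and the base-case power do not change. The stated worst case becomes less favourable.

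### The power table behind n=36 is for time to first bowel movement rather than paralysis, and its 70/40 column repeats the 80/50 column

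*SAP*

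**What the plan says.** SAP 12.2.2 (with the same table and statement in protocol 12.2.2) reads day-4 rates of failure to defecate from a published Kaplan-Meier plot. It says this rate "was used as the estimate of lower GI tract paralysis", and it links the rate to the endpoint in one sentence: "We believe the 4-day estimate will be strongly related to the primary outcome of lower GI tract paralysis". The columns are headed "Proportion Failing to Defecate at Day 4 (Placebo vs. Prophylactic Treated". For assumed values of 90% on placebo and 40% on treatment, with complete follow-up and a log-rank test, the text claims that "this sample size yields over 95% power using an alpha of 0.05 if the true day 4 estimated freedom of event (defecation) rates are" those values. For incomplete follow-up it adds: "we have shown the impact on the power if approximately 20% of subjects do not finish the study".

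SAP 12.2 defines the primary analysis differently. It is a log-rank test of "time to first development of lower GI tract paralysis", meaning at least 3 days "without a SBM after study randomization) during the ICU stay up to 10 days". If every subject completes, it becomes a chi-square test of proportions. First bowel movement appears only as a secondary outcome: "The secondary outcome, time to first SBM will be estimated using a Kaplan Meier time to event analysis".

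**The concern.** Defecation and paralysis are different events. One test counts patients who pass stool; the other counts patients who go at least 3 days without doing so. Log-rank power depends on the number of events and on the hazard ratio for the event being tested, so a strong relation between two outcomes does not carry power from one to the other. The plan computes power for the secondary event and uses it to support the sample size for the primary one, with no conversion.

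A second problem concerns the table itself. The 80/50 and 70/40 columns agree to the decimal in all four rows (76.0, 84.9, 72.5 and 82.2%), although the two scenarios imply different hazard ratios and event counts.

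The table is the only quantitative support for n=36, and its smallest entry is 72.5%. A reader would conclude that the primary comparison is well powered across the planned range, and would read a null primary result accordingly.

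**Working it through.** **Inputs.** From SAP 12.2 and 12.2.2: 18 per group; two-sided alpha 0.05, with 0.10 as the alternative; day-4 proportions without an SBM (placebo/treated) of 90/40, 90/50, 80/40, 80/50 and 70/40; a primary analysis period of up to 10 days. The table states no horizon or survival shape. I assume constant hazards and infer the horizon by fit.

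**Step 1: reproduce the table with defecation as the event.** With S the day-4 proportion without an SBM:

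- hazard = −ln(S)/4, so HR = ln(S_treated)/ln(S_placebo)
- events by day 10: d = 18 × [(1 − S_placebo^2.5) + (1 − S_treated^2.5)]
- power (Schoenfeld) = Φ(½√d × ln HR − 1.96)

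At 90/40: HR = 0.9163/0.1054 = 8.70; d = 18 × [(1 − 0.768) + (1 − 0.101)] = 20.35; ½√20.35 × ln 8.70 − 1.96 = 2.92; power 99.8%.

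| Alpha 0.05, full completion | 90/40 | 90/50 | 80/40 | 80/50 | 70/40 |
|---|---|---|---|---|---|
| Hazard ratio | 8.70 | 6.58 | 4.11 | 3.11 | 2.57 |
| Events by day 10 | 20.35 | 18.99 | 23.87 | 22.51 | 26.80 |
| Recomputed power, % | 99.8 | 98.4 | 93.2 | 76.7 | 68.5 |
| Stated power, % | 99.8 | 98.4 | 92.7 | 76.0 | 76.0 |

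Over all four rows of the table, the first four columns agree within 0.8 points at 10 days and within 0.6 points at 9.5 days. The table is therefore for time to first SBM.

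**Step 2: the 70/40 column.** At 10 days, ½√26.80 × ln 2.57 − 1.96 = 0.48, giving 68.5%. For horizons of 9 to 11 days, 80/50 gives 74.4-78.6% and 70/40 gives 66.6-70.1%. At day 4, the only day the SAP states, they are 52.1% and 47.6%. No horizon tested makes the columns equal. Down the four rows the 70/40 column would be about 68.5, 78.7, 65 and 76% at 10 days, against the stated 76.0, 84.9, 72.5 and 82.2%.

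**Step 3: paralysis as the event.** The documents give no paralysis incidence, so I used two assumptions.

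- *A*: incidence equals the day-4 proportions, following the SAP's own premise.
- *B*: incidence equals the 72-hour rate without an SBM implied by constant hazards, S^0.75. At 90/40 this is 92.4% vs 50.3%.

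The chi-square power is exact, by enumeration without continuity correction. The log-rank power is simulated (20,000 runs, standard error at most 0.4 points) for three event timings.

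| Power %, alpha 0.05, full follow-up | 90/40 | 90/50 | 80/40 | 80/50 | 70/40 |
|---|---|---|---|---|---|
| Stated | 99.8 | 98.4 | 92.7 | 76.0 | 76.0 |
| A, chi-square | 92.7 | 78.5 | 74.2 | 49.8 | 49.3 |
| A, log-rank, all events at 72 h | 92.8 | 78.0 | 74.7 | 50.3 | 50.0 |
| A, log-rank, constant hazards days 3-10 | 95.2 | 84.6 | 74.8 | 52.4 | 46.7 |
| A, log-rank, uniform days 3-10 | 89.1 | 73.2 | 68.7 | 44.5 | 43.3 |
| B, chi-square | 84.6 | 67.1 | 62.1 | 38.9 | 39.8 |
| B, log-rank, same three timings | 79-91 | 59-78 | 57-67 | 35-46 | 36-41 |

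A closed-form check under A at 90/40: HR = ln(0.6)/ln(0.1) = 0.222; d = 18 × 1.3 = 23.4; Schoenfeld power 95.4%.

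**Step 4: the other rows.** At alpha 0.10 with full follow-up, A gives about 94-98% at 90/40 (stated 100.0%), 57-65% at 80/50 and 56-63% at 70/40 (both stated 84.9%). With 20% loss at alpha 0.05, either before 72 hours or spread over 10 days, A gives about 81-92% (stated 99.7%), 37-48% and 35-42% (both stated 72.5%). Early loss is plausible: protocol 4.1 requires only an expected stay of at least 48 hours, protocol 2.1 ends follow-up at ICU discharge, and the event needs 72 hours to occur.

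**Step 5: paralysis after an early SBM.** This also counts as a primary event, and the documents give no rate for it. Adding it to A for 10-30% of early responders in both arms lowers chi-square power at 90/40 to 87.4-72.6%. Adding it in placebo only raises it to 94.0-96.1%, still below the stated figure; the same holds in the other four columns.

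**The case against.** The proxy is disclosed. The SAP names defecation as the event and calls the link to paralysis a belief, and its sentence about power is conditional on defecation rates. Read literally, that sentence is right: the recomputation also gives 99.8%. This stands, and it means the defect is a missing conversion, not a concealed or false statement.

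The size of primary power is also uncertain. Under A, patients with no SBM by day 4, counted from randomization, have all reached 3 days at 72 hours, so spreading events uniformly to day 10 fits that premise poorly; yet it supplies the low ends of the A ranges. The 72-hour timing alone gives 92.8% at 90/40 and about 50% at 80/50 and 70/40. A more favourable reading, with paralysis accruing at a constant hazard to day 10 from the day-4 rates, gives Schoenfeld power of 98.7/93.0/88.8/67.0/65.2%. That is above 95% at 90/40 but still below the stated figure in every column.

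Power can exceed the stated figure if late paralysis is added in placebo alone: 78.7% at 70/40 when 40% of early responders are affected, and 78.5% at 80/50 when 50% are. Those cases change the scenario itself, to 82 vs 40 and 90 vs 50. The claim that power is lower is therefore not universal, but it holds for the incidences the SAP puts forward.

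Finally, this is a proof-of-concept study that openly contemplates alpha 0.10, and base-case power remains high. That limits the consequence. None of these points touches the repeated column.

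**Conclusion.** The concern holds. Two parts do not depend on modelling the primary endpoint: the table's event is first defecation, a secondary outcome, and the 70/40 column cannot equal the 80/50 column. The corrected 70/40 values are indicative only, because the horizon, software and loss model are not stated.

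For the primary endpoint, taking the day-4 proportions as paralysis incidence with no late paralysis, power at alpha 0.05 and full follow-up is about 89-95% at 90/40, and about 43-52% at 80/50 and 70/40. More than 95% power at the base case is not reliably met, but the shortfall there is modest. The material gap is in the two weakest planned scenarios, where the chance of detection is about even instead of 76%. This affects how a null primary result should be read; it does not affect the conduct of the trial.

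**What to change.** Keep n=36. In SAP 12.2.2 and protocol 12.2.2, recompute the table with paralysis as the event. State the assumed incidence, event timing, horizon and timing of loss, and include loss before 72 hours as one case. Replace the claim of more than 95% power with the resulting range; at 90/40, alpha 0.05 and full follow-up this is about 89-95% under A and 79-91% under B.

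If the existing table is kept, label it as power for time to first SBM (secondary outcome) and give its horizon. Say that power for paralysis is lower under the stated assumptions, and recompute the 70/40 column with the original software and inputs.

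The cost is one recalculated table and some wording in two places. Sample size, endpoint, tests and patient procedures do not change. The stated power becomes less favourable.
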